11.6. Sample Size Justification

For the first co-primary endpoint, it is expected that approximately 90% of participants receiving usual care will be prescribed an antibiotic during the 28 days of primary outcome follow-up. A clinically meaningful and feasible reduction in the proportion of those prescribed antibiotics is considered to be 15%. Therefore, 100 participants per arm will be required for 80% power (and 133 subjects for 90% power)

to detect an improvement of 90% to 75% in antibiotic prescribing for each CA-ARTI-Dx hypothesis vs. usual care, respectively, using a traditional two-sided 0.05 Type I error.

For the second co-primary outcome, we assume an exponential time to recovery with a mean of 4 days (based on ALICE data). Under the exponential distribution, a mean increase of 1 day is equivalent to a hazard ratio of 0.80. Hence, to demonstrate no worse than a mean 1 day increase in time to recovery (or equivalently a hazard ratio no less than 0.80) within 28 days of follow-up, 318 patients per group are required to provide 80% power using a traditional two-sided 0.05 Type I error for each CA-ARTI-Dx hypothesis vs. usual care.

Given the very high power for the first co-primary endpoint (reduction in prescribing of antibiotics), the power for the joint co-primary hypothesis is essentially equal to the statistical power of the second coprimary endpoint (time to recovery), which is approximately 93% or greater power across the two seasons for each CA-ARTI-Dx, and approximately 69% or greater probability of obtaining superiority after one season (see appendix F).

Given the wide range of uncertainty in the above assumptions underlying these calculations, we propose to conduct a simulation study to further characterize the statistical power of the design and to refine the decision criteria. The virtual trial simulations will explore the impact of the assumed control group distributions of antibiotic prescriptions and time to recovery, distribution of participants across strata (primary symptom, flu season), the expected CA-ARTI-Dx effects, the extent of missing data, differing accrual rates between winter seasons, and varying correlation between endpoints. In addition, the simulations will incorporate a single interim analysis to evaluate the primary hypotheses in between winter seasons, and explore the possibility/likelihood of evaluating additional CA-ARTI-Dx in the second winter season.

Further sample size justification is given in appendix F for the specific CA-ARTI-Dx tests under evaluation.

11.7. Adaptive Arm Stopping and Addition of New Arms

The trial will continue through two winter seasons of CA-ARTI (typically October to May), and each winter season will encompass a shorter influenza season (length varies by year). A single interim analysis will be conducted in between winter seasons, in which both of the co-primary endpoints are evaluated for each of the CA-ARTI-Dx. If early success or futility is determined for either CA-ARTI-Dx relative to usual care, a new CA-ARTI-Dx will replace the given CA-ARTI-Dx in the second winter season. Otherwise the given CA-ARTI-Dx will be continued in the second CA-ARTI season. The co-primary endpoints and primary analyses will remain the same for any newly introduced CA-ARTI-Dx arms. Decision rules for claiming superiority of a given CA-ARTI-Dx upon conclusion of either winter season will be calibrated to control the overall Type I error for each CA-ARTI-Dx at the approximate one-sided 0.025 level. These thresholds will be pre-specified. Any additional CA-ARTI-Dx introduced in the second winter season will require a statistical Appendix/Addendum to update the SAP.

11.8. **Analysis populations**

The primary analyses will include all participants in the intention to treat (ITT) population, i.e. all participants randomized and analysed in their respective randomized assignment. Additional populations

will be described in the SAP; this includes all participants who underwent the intervention (a safety population); all eligible participants (a per protocol analysis); and an "as treated" population.

11.9. Procedure for Accounting for Missing, Unused, and Spurious Data.

For a given endpoint, the primary analyses will be conducted using complete cases, i.e. ignoring patients with missing endpoints. Sensitivity analyses will be conducted exploring the impact of missing data and any biases that may be present.

11.10. Secondary Endpoints & Analyses

The secondary endpoints and analyses of the study are fully described in a statistical analysis plan (SAP) and will be available prior to any interim analyses.

11.11. Cost Effectiveness Analysis

Cost-effectiveness analysis (CEA) will compare the direct medical costs, productivity costs, and health outcomes (in terms of days on antibiotic regime, doses of antibiotics prescribed, number of days where CA-ARTI limits usual activities and Quality Adjusted Life Years gained) between the CA-ART-Dx arms and the routine care arm. The analysis will source data from the trial (resource use, EQ-5D-5L and VAS scores), and use other relevant data from the countries in which the trial is set (e.g., unit costs, and type of health care provided within each country if available information is obtained from each country, otherwise unit costs would be estimated as a range for all participant countries).

Uncertainty will be explored using sensitivity and subgroup analyses. Value of perfect information analysis may also be performed to identify which sources of uncertainty should be reduced through additional research to efficiently improve decision making.

These analyses will be conducted after each season, and depending on the evolution of the trials' arms, the comparators may change accordingly.

11.12. Process Evaluation Analysis

Qualitative data collection and analysis will be done concurrently. Interviews with clinicians and patients, will be analysed using thematic and framework analysis taking an inductive approach (1-3). NVivo software will be used to assist with the organisation of data. A thematic framework will be used to chart data across all interviews and will aid comparisons between participants.

Quantitative data from surveys with clinicians and patients will be analysed using descriptive statistics.

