2)	Patient/parent views of CA-ARTI-Dx and how they impact consultations including patient satisfaction and intention to consult in future for similar symptoms.	2)	Interviews and surveys with patients.		

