9.9. Subsequent Visits

There is no requirement for participants to have a research-specific face-to-face follow-up visit as part of their study participation, as all subsequent measurements consist of self-completed questionnaires or through telephone calls by the trial team (including process evaluation interviews for some of the participants).

Participants (or their legal guardian or their carer) will be asked to complete a simple, user-friendly diary each day until they have returned to usual activity for two consecutive days, or up to day 14 (whichever is sooner), the diary will request the following information:

- Employment status
- Return to usual activities each day
- Antibiotic use
- Use of other prescription medication
- Individual symptom severity
- Health care resource use, including hospitalisation
- Use of over-the-counter and non-prescription medication or remedies
- Out-of-pocket expenditure
- Number of work/school/nursery days lost
- EQ-5D-5L (or alternative as recommended for age) and Visual Analogue Scale (VAS) (Day 1, Day 14 and Day 28)
- Patient Enablement Instrument (Day 1)

• Process evaluation patient survey (see section 9.10) (Day 1)

The diary will be available on-line (study team preferred option) and in a paper version for posting back to the national network coordinator when specifically requested or where the participant does not have daily access to the internet.

Participants who have not completed/returned their diary by day 14 will be telephoned on or after day 14 (+ 3 days) by the study team and asked a brief set of questions to establish a minimal data set including antibiotic use, day returned to usual activity, hospitalisation, COVID-19 testing and EuroQoL EQ-5D. All participants will be telephoned again on or after day 28 (+ 3 days) regarding antibiotic use, day returned to usual activity if not already stated by day 14, hospitalisation, COVID-19 testing and EuroQoL EQ-5D in the preceding 14 days. We will also repeat the brief process evaluation patient survey (see section 9.10). The study team will attempt to call the participant no more than 3 times on each occasion.

Participants may receive reminder text messages about these telephone calls and to return the diary if they give the trial team their mobile telephone number.

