9.11. Nested Process Evaluation

A mixed-methods process evaluation will be nested within the trial. The process evaluation will capture data to understand how the intervention is used and viewed by clinicians and patients in order to explain how clinicians and patients adopt CA-ARTI-Dx in community care. Not all countries included in the PRUDENCE study will participate in the Nested Process Evaluation Interviews. See appendix G for the current list of participating countries.

Interviews:

4-5 countries from the 12 that participate in the trial will be used as case studies that reflect diversity in relevant factors such as healthcare system, community care settings, income, geographic location in Europe and antibiotic use.

We will carry out interviews (telephone, online (e.g. using Microsoft Teams or face to face as appropriate) with patients participating in the trial throughout the recruiting period. All patients will be eligible to take part in an interview unless they do not have capacity. Interviews will capture experiences of and satisfaction with care when a CA-ARTI-Dx is used and subsequent views and experiences of management of symptoms (including antibiotic use). Some patients recruited to intervention arms in the trial (approximately 8-10 per country) will be purposively sampled across recruiting periods to give a total of 32-50 interviews. We will seek to obtain variation in age, symptom presentation, type of CA-ARTI-Dx carried out and whether an antibiotic is prescribed. Parents/carers of child patients under 12 will be invited to interviews. Patients aged 12 years and older will be invited to interviews, with parents able to sit in on interviews with children under 16 where desired. Patients will be provided with Patient Invitation Letter and Patient PIL. We will obtain written or oral consent prior to an interview. A password protected copy of the consent will be emailed to participants.

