In addition, we will conduct (telephone, online (e.g. using [name]) or face to face as appropriate) interviews with healthcare professionals to capture experiences using CA-ARTI-Dx in daily clinical practice, and identify any additions and improvements required when rolling out CA-ARTI-Dx and any training materials during the trial in order to meet clinicians' and patients' needs and support use. Any health professionals supporting PRUDENCE will be eligible to take part and CIs at each site will identify and invite professionals. Different health professionals (approximately 7 per country, each representing a participating practice/faculty) will be purposively sampled across each of the recruiting periods to give a total of 28-35 interviews. We will seek to obtain variation in professional role, practice setting, and experience. Healthcare professionals will be provided with Clinician Invitation Letter and Clinician PIL. We will obtain written or oral consent prior to an interview. A password protected copy of the consent will be emailed to participants.

Semi-structured topic guides will be informed by existing literature and theory, including the Theoretical Domains Framework and the Common Sense Model, to ensure that questions elicit likely key determinants of behaviour, and Normalization Process Theory to identify how POCT diagnostics could be embedded in routine practice. Data will be analysed using thematic and framework analysis (1, 2).

Surveys:

Surveys will assess the views of clinicians and patients on the use of CA-ARTI-Dx in ARTI consultations, examine how CA-ARTI-Dx are implemented and experienced.

Patient surveys will be included in the participant diary on Day 1 and in the follow-up telephone call at Day 28 (as described above). Surveys will include brief statements measuring patient satisfaction with the consultation, beliefs about the necessity of antibiotics for respiratory symptoms and future behavioural intentions to manage symptoms and (re)consult for future illness. Patient surveys will be included for all participants in all trial sites.

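### Section 11.12 plans only description of the patient survey, though its objective asks about impact and the survey covers every randomised arm; no stratum-matched comparison with usual care is stated

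*Protocol*

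**What the plan says.** Section 6 lists, among the process evaluation objectives, "Patient/parent views of CA-ARTI-Dx and how they impact consultations including patient satisfaction and intention to consult in future for similar symptoms". The stated source is "Interviews and surveys with patients".

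Section 9.11 describes the survey: "Surveys will include brief statements measuring patient satisfaction with the consultation". It also covers beliefs about the need for antibiotics and intentions for managing or consulting for future illness. On coverage it says "Patient surveys will be included for all participants in all trial sites", which includes usual care. The survey is in the Day 1 diary, and Section 9.9 says of the Day 28 call "We will also repeat the brief process evaluation patient survey".

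The analysis is fixed in Section 11.12: "Quantitative data from surveys with clinicians and patients will be analysed using descriptive statistics". No comparison by arm, adjustment or interval is named.

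Appendix F sets which tests are allocated in which strata. CRP is offered only to participants with predominant cough. Veritor is offered to sore-throat participants all season, but to cough participants only in flu season. Usual care is an option in every stratum.

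**The concern.** Asking "how they impact consultations including patient satisfaction and intention to consult in future for similar symptoms" is a question about effect, and an effect needs a comparator. Section 9.11 describes the purposive interview sample as patients recruited to the intervention arms, so within the process evaluation the survey is the source that plainly includes usual care. If it is only described, the impact part of the objective has no planned contrast and no statement of uncertainty.

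The allocation scheme adds a second problem. Because the arms contain different mixes of cough and sore throat, a reader who subtracts one arm's percentage from another's compares different kinds of patient. Section 11.5 guards the co-primary analyses against this by adjusting for primary symptom and flu season. Section 11.12 gives the survey no such protection.

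**Working it through.** **Inputs (Appendix F).** 1250 participants per winter season; 50% cough; 50% enrolled in flu season; 5% missing the primary endpoint; allocation ratios by stratum.

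**Reproducing the plan's arm sizes.** 1250 × 0.95 = 1187.5 analysable, or 1187.5 / 4 = 296.9 in each of the four strata.
- CRP: (1/3 + 1/2) × 296.9 = 247.4, stated as 247.
- Veritor: (1/3 + 1/2 + 1/2) × 296.9 = 395.8, stated as 395.

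Both figures agree with the protocol.

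**Share of cough in each arm, in units of one stratum.**
- CRP: 5/6 in total, all cough, so 100%.
- Veritor: 4/3 in total, of which 1/3 is cough, so 25%.
- Usual care: 1/3 + 1/2 + 1/2 + 1/2 = 11/6 in total, of which 1/3 + 1/2 = 5/6 is cough, so 5/11 = 45.5%.

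**What an unstratified table would show with no true effect.** Suppose agreement with an item differs by d points between cough and sore throat. The protocol gives no d, so the values below are assumptions.
- Spurious CRP minus usual care = (1 − 0.4545) × d: 2.7 points at d = 5, 5.5 at d = 10, 10.9 at d = 20.
- Spurious Veritor minus usual care = (0.25 − 0.4545) × d: −1.0, −2.0 and −4.1 points.

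The two errors have opposite signs, so the table would also distort how the tests look beside each other.

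**What a matched comparison removes.** In every stratum where a test is an allocation, the ratio of that test to usual care is 1:1. Restricting usual care to those strata therefore restores the balance of symptom and season. Adjustment for the two factors then follows the approach of Section 11.5.

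**Precision of the matched comparison.** The 95% CI half-width for a difference in proportions is 1.96 × √(2p(1−p)/m), where m is the stated arm size times the response rate. The protocol gives neither response nor agreement, so I took response of 60-100% and p of 50-90%.

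| Comparison | Per arm | Best case (100% response, p = 0.9) | Worst case (60% response, p = 0.5) |
|---|---|---|---|
| CRP, one season | 247 | 5.3 points | 11.4 points |
| CRP, two seasons | 494 | 3.7 points | 8.1 points |
| Veritor, one season | 395 | 4.2 points | 9.0 points |
| Veritor, two seasons | 790 | 3.0 points | 6.4 points |

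Example: CRP, one season, worst case: m = 247 × 0.6 = 148.2, and 1.96 × √(0.5/148.2) = 0.114.

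The one-season rows matter because Section 11.7 allows either test to be replaced after the first winter.

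**The case against.** The strongest reply is that nothing here is an error. The survey sits in a nested process evaluation whose aim is given as "The process evaluation will capture data to understand how the intervention is used and viewed by clinicians and patients". Its objectives are listed apart from the co-primary and secondary ones, interviews serve the same objective, and no hypothesis or decision rests on it. Describing such data is common and defensible. Actual re-consultation, antibiotic use and the Patient Enablement Instrument are secondary outcomes whose analysis Section 11.10 assigns to the SAP. Most of this stands, and it is why the point is minor.

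Section 11.1 also says that Section 11 is a summary with detail in the SAP, so a by-arm layout may be specified there. That weakens the point without answering it. Section 11.10 defers to the SAP expressly, whereas Section 11.12 names a type of analysis.

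It can also be said that no passage proposes an unstratified table. That is correct. The confounding is a risk the wording leaves open, not something the protocol plans.

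Two stronger readings are tempting, and the documents support neither.
- A reader might infer that the objective gets no estimate at all. Descriptive statistics are means and proportions, and nothing stops them being tabulated by arm. What is missing is a planned, matched difference with its uncertainty.
- A reader might infer that randomisation would answer the question without bias. The trial is open (Section 9.6), the answers are self-reported after allocation is known, and the Day 28 survey depends on a call attempted at most three times (Section 9.9). Response could differ by arm, and an interval would not capture that.

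**Conclusion.** The point holds as a minor improvement. Section 11.12 limits to description the one process-evaluation source that clearly includes usual care, although the objective asks about impact. An unstratified by-arm table would be confounded by symptom: 100% cough for CRP, 25% for Veritor and about 45% for usual care, given the Appendix F assumptions of half cough and half flu season.

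The half-widths tabulated above would make a matched comparison informative at the trial's present size, but they depend on assumed response and agreement rates. Quoting only the full-response, two-season values at 50% agreement (6.2 points for CRP, 4.9 for Veritor) would overstate what can be relied on.

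A reader might also infer that stated intentions decide later antibiotic use. The documents offer no evidence for that, and the point does not need it. Nor does it extend to the clinician survey, which is taken before and after recruitment at a site and has no randomised comparator. The co-primary conclusions are unaffected.

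**What to change.** Add to Section 11.12, for the patient survey:
- Items on satisfaction, belief in the need for antibiotics and intention to consult are summarised by randomised arm at Day 1 and Day 28.
- Each test is compared with usual-care participants from the strata where that test was an allocation, adjusted for primary symptom and flu season.
- Differences are reported with 95% CIs and labelled exploratory, with the response rate shown by arm.

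The cost is a little analysis work, with no new data and no more participants. Three constructs, two time points and two tests make 3 × 2 × 2 = 12 contrasts without multiplicity control, so none can carry a confirmatory claim. The limits of an open trial with self-reported answers should be stated beside the results.

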12. DATA MANAGEMENT

The data management aspects of the study are summarised here with details fully described in the Data Management Plan.

12.1. Source Data

Source documents are where data are first recorded, and from which participants' CRF data are obtained. These include, but are not limited to, hospital records (from which medical history and previous and concurrent medication may be summarised into the CRF), clinical and office charts, laboratory and pharmacy records, diaries, microfiches, radiographs, and correspondence.

CRF entries will be considered source data if the CRF is the site of the original recording (e.g. there is no other written or electronic record of data). All documents will be stored safely in confidential conditions. On all study-specific documents, other than the signed consent, the participant will be referred to by the study participant number/code, not by name.

12.2. Access to Data

Direct access will be granted to authorised representatives from the Sponsor and host institution for monitoring and/or audit of the study to ensure compliance with regulations.

12.3. Data Recording and Record Keeping

Research Online (RO) is an electronic data capture (EDC) system that will be used for data collection. Webbased case report forms (eCRF) are implemented into the system to facilitate the study-specific data collection. These forms can easily be accessed by all standard web browsers. The baseline CRF, Symptom Diaries, Days 14 and 28 phone questionnaires and SAE Forms will be entered onto this system.

Multiple validation and range checks will be programmed in the eCRF to assure complete and high-quality data. Data that does not comply with these rules or ranges will generate a query that must be resolved immediately or at a later stage. Electronic workflows will employ multiple skip and jump rules to ensure that only information that is applicable to the patient will appear. After the data of the last subject is entered, the database can rapidly be closed and data made available for cleaning, further analysis and publication purposes.

RO meets all requirements according to GCP standards for electronic data entry with respect to safeguarding data integrity and data security regulations. Users will have role-based access to the system by logging in using their personal username and password. The system will log all data entry steps with timestamps and user information. The role-based access to the system will avoid unauthorised data access and prevents users from performing actions that they do not have authorisation for.

Project management and monitoring of the study is facilitated by the integrated real live study progress reports. RO data traffic over the Internet is encrypted using secured data communication protocols. Dedicated databases and web servers are hosted in a secure data centre, the database (PostgreSQL) is backed up on a daily basis.

For process evaluation interviews:

Each interview will be audio-recorded with the participant's permission. Recordings will allow verbatim transcription of interviews in Microsoft Word. Transcription will be completed by an independent transcriptionist who holds a contract with a partner university. If any interview is conducted in a language other than English recordings will be transcribed and translated by a member of the research team or by an independent transcriptionist and translator who holds a contract with a partner university. Once transcribed and transcripts are checked, recordings will be deleted. Transcripts will be labelled with a

unique participant number and will omit any identifiable data either identifying the participant or their general practice.

